Although severe adverse events and deaths during stabilisation of the critically ill child are uncommon, these events can profoundly affect patients, families, and hospital staff. For hospital staff—particularly less experienced resident doctors and junior nurses—the moral injury incurred can be great. Higher rates of adverse airway management events during stabilisation have been reported in non-tertiary hospitals than in tertiary hospitals which suggest the moral injury to staff may be incurred more in non-tertiary hospitals. In addition, there is evidence of inconsistent access to post-incident support for families and healthcare staff, which can exacerbate emotional distress and contribute to long-term psychological impact.

Only around 11% of hospitals where children may present have on-site paediatric critical care facilities and just 23% of hospitals without a PICU have specialist paediatric anaesthetic cover. Data from PICANet shows an increase in the transfer of low acuity children to PICUs, potentially reflecting some non-tertiary hospitals' reticence in managing children due to limited, or no, on-site specialised paediatric specialty cover. 9

There are also significant organisational challenges to delivering effective stabilisation care for critically ill children in non-tertiary hospitals, including poorly defined referral pathways to tertiary care, inconsistent lines of communication between secondary and tertiary hospitals, access to acute imaging, and variable implementation of escalation frameworks such as Paediatric Early Warning Systems (PEWS) and Martha's Rule. These organisational gaps can result in delays in recognising deterioration, initiating timely interventions, and arranging appropriate transfers to specialist centres. 10,11

This study will aim to identify examples of both good and poor practice in the care provided to children who require stabilisation while in hospital and assess critical care training among non-specialist healthcare providers and support from tertiary centres, and the impact of stabilisation processes on healthcare teams and families. The end report will inform strategies designed to standardise clinical practice, enhance patient outcomes, and strengthen support mechanisms for patients, families and healthcare professionals.

Guidelines and standards

- Royal College of Paediatrics and Child Health, 2018. Facing the Future: Standards for Children in Emergency Care Settings. https://www.rcpch.ac.uk/sites/default/files/2018-06/FTFEC%20Digital%20updated%20final.pdf
- Royal College of Paediatrics and Child Health, 2014. High Dependency Care for Children – Time To Move On. https://www.rcpch.ac.uk/sites/default/files/2018-07/high-dependency-care for-children - time-to-move-on.pdf

Aim and objectives

Aim

- To identify good practice and areas for improvement in the quality of care provided to patients 0-18th birthday who are critically ill and require stabilisation
- To review the impact of delivering that care on staff, patients and parent carers

Objectives

Organisational issues

Data to be collected from the organisational questionnaire

To review the organisation of services for patients who are critically ill and require stabilisation, including:

- The organisation of services (including type of organisation, staffing arrangements, access to PHDU/HDU/PICU/ICU, the size of the paediatric unit)
- The availability of/access to decision making tools (e.g. Paediatric Early Warning Systems (PEWS))
- Protocols, pathways of care, and the use of guidelines and apps
- Networks of care (including shared decision making between organisations)
- Transfer arrangements (including methods of transport, time to nearest PHDU/HDU/PICU/ICU, location of transfers)
- The availability of staff (including competency and the ability to maintain skills, e.g.,
 if the number of cases is low, the availability of Paediatric Critical Care Outreach
 (PCCO)/ Critical Care Outreach teams (CCOT), support from adult ICU)
- The appropriateness of care settings (including criteria for where patients are cared for)
- The availability of equipment
- Access to diagnostics (imaging)
- Access to therapy (including paediatric respiratory physiotherapy)
- Moral injury staff sickness and retention, debriefing including access to psychological support and counselling
- The availability of information for staff (including access to different patient administration systems within and between hospitals)
- The availability of information, support services and facilities for patients and parent carers
- Training, education and the retention of skills
- Audit (including the use of the Patient Safety Incident Response Framework (PSIRF), and shared information across organisations)
- The use of Martha's Rule¹⁰ (where applicable), or equivalent

Clinical issues

Data collected from the clinical questionnaire, the reviewer assessment form and clinician survey.

To explore:

- The initial recognition for the need for stabilisation (including source of referral, triage and location of care)
- The assessment process (including investigations and specialty review)
- The stabilisation process (including communication, staff involved in the stabilisation process, equipment available, and whether the patient had the appropriate intravenous access and respiratory support)
- Staffing arrangements (including the grade/specialty of clinicians assessing, diagnosing and treating/stabilising patients)

- The decision-making process (who was involved, was it timely, were there ceiling of treatment conversations)
- The use of decision-making tools and guidelines/protocols/apps (e.g. Martha's Rule, PEWS) (including network support)
- Transfer arrangements (including the decision-making process around which
 patients were transferred or not, why they were/were not transferred and whether
 this was appropriate)
- Moral injury workforce and parent carer thoughts and feelings (clinician, patient & parent carer survey)

Methods

Inclusion criteria

Patients aged 0 to 18th birthday, who require stabilisation in hospital between the 1st October 2024 – 31st March 2025 (admission may have been prior to this date). Patients will be identified for inclusion from hospital patient administration systems and via paediatric critical care transport team records.

Via hospital patient administration systems

Local reporters will be asked to populate the patient identification spreadsheet with the details of patients who were:

- Admitted to critical care (level 2 (PHDU/HDU) or level 3 (PICU/ICU) care)
- Seen in the Emergency Department and have one of the included SNOMED CT or OPCS codes (listed below):
- Transferred to another hospital

If any one of the three criteria above are met, the patient should be included on the patient identification spreadsheet

SNOMED CT/OPCS codes for inclusion

	SNOMED CT code	OPCS code	
General anaesthesia	50697003	Y80	
Non-invasive ventilation	428311008	E85.2	
Insertion of endotracheal tube	112798008	X56.2	
		X56.9	
Insertion of catheter into artery	392247006	L70.4	
Central venous cannula insertion	233527006	L91.2	
		Y53.9	
Intraosseous cannulation	430824005	Y33.0	

Via paediatric critical care transport team records

Local reporters in the Trusts/Health Boards where the paediatric critical care transport teams are based will be asked to populate the patient identification spreadsheet with the details of patients who were:

- Discussed with a critical care/paediatric transport/retrieval team during stabilisation
- Transferred by a critical care/paediatric transport/retrieval team

Exclusions

 Patients admitted to the Neonatal Intensive Care Unit (NICU) or Special Care Baby Unit (SCBU)

- Patients who are admitted as a result of trauma (ICD10 codes T00 T88) to a major trauma centre (patients admitted as a result of trauma to a non-major trauma centre will still be included)
- Patients admitted to independent hospitals

Data sampling time frames

The timeframe from which data will be sampled will be between the 1^{st} October $2024 - 31^{st}$ March 2025.

Participating providers of healthcare

All acute hospital providers where patients might be admitted will be asked to participate in the study.

Incidence and prevalence of the exemplar conditions

The State of the Nation report, 2024 (Paediatric Intensive Care Network: PICANet) identified 18,498 admissions to PICU in 2023 (approx. 50 admissions a day or 1,542 admissions a month).

Early scoping has identified 828 patients admitted to PHDU/HDU/PICU/ICU from 54 Trusts/Health Boards over a one-month period. This is an average of 15.3 per Trust/Health Board per week (range, 0-104; median, 3; Mode, 0). Based on data returns from 125 Trusts/Health Boards, this would identify approximately 1938 patients per month for inclusion in the study. Based on the range of patients identified from each Trust/Health Board, data will be collected over a six-month period to ensure patients are identified from centres where a smaller number of patients are admitted.

Study promotion

Prior to data collection, NCEPOD will contact all hospitals and paediatric critical care transport teams providing care to this group of patients. The study will also be promoted via NCEPOD Local Reporters (sending the study poster on to the relevant departments), the relevant Colleges and Associations, and any relevant patient groups and third sector organisations.

Study method test

The data collection methods and data collection tools will be tested to ensure they are robust before the full study is run.

Methods of data collection

There will be five main methods of collecting data for the study:

- Patient and parent carer views will be collected through focus groups and an online anonymous survey. We will work with Local Reporters, and relevant charities (e.g. WellChild, Together for Short Lives, Child Bereavement UK, Cosmic) to encourage involvement.
- 2. Clinician views will be collected through an online anonymous survey. We will work with Local Reporters and study contacts to encourage involvement from clinicians.
- 3. An organisational questionnaire will be sent for all acute hospitals where patients might present.

- 4. Clinical data collection retrospective data collection: For a sample of patients, a questionnaire will be sent to the clinician responsible for the patient at the time of admission (stabilisation questionnaire), and to the team who received the patient for their definitive critical care admission (critical care questionnaire) (where applicable)
- 5. Case note review: Copies of selected extracts of case notes will be collected for peer review.

Further details on the methods of each method of data collection are given below.

1. Anonymous online patient and parent carer surveys and focus group interviews

The survey and focus group interviews will gather data on the parent carer views of the services available to them. It will also collect information around support services and information and facilities available to parent carers of young people who require stabilisation. The data will not be linked to any other aspects of data collection.

2. Anonymous online clinician survey

The survey will gather data on clinician views of the services available for them to provide to patients who require stabilisation. It will also collect information around confidence, competency, training and support available when providing care to this group of patients. The data will not be linked to any other aspects of data collection.

3. Organisational questionnaire

Data will be collected at a hospital level and will collect information around decision making tools, the organisation of services, protocols and pathways of care, networks of care, transfer arrangements, staffing arrangements, the appropriateness of care settings, the availability of equipment, diagnostics and radiology, moral injury, the availability of information, training, and audit and data collection. Questionnaires will be sent to all hospitals participating in the study via the online questionnaire system.

4. Clinical data collection – retrospective data collection Patient identification

Two patient identification spreadsheets will be used to collect data for this study; one which identifies patients for inclusion via hospital patient administration systems (to be sent to all participating Trusts/Health Boards), and one which identifies patients via paediatric critical care transport teams records. The transport team spreadsheet will only be sent to the Trusts/Health Boards where the paediatric transport team are based (15 across England, Wales and Northern Ireland)

The Local Reporter will be asked to complete the patient identification spreadsheet with the details of all patients:

Via patient administration systems

- Admitted to critical care (level 2 (PHDU/HDU) or level 3 (PICU/ICU) care)
- Seen in the Emergency Department and have one of the included SNOMED CT or OPCS codes (listed above)
- Transferred to another hospital

Via paediatric critical care transport teams

- Discussed with a critical care/paediatric transport/retrieval team during stabilisation
- Transferred by a critical care/paediatric transport/retrieval team

The data fields requested in the patient administration system spreadsheet will include NHS number, hospital number, date of birth, sex, postcode, emergency department attendance details, date of admission, source of admission (including name of transferring hospital where applicable), SNOMED CT, ICD10 and OPCS codes, critical care admission details, discharge destination, date of discharge, clinician code and specialty for the clinician responsible at the time of admission, clinician code and speciality for the clinician responsible for receiving the patient into critical care (where applicable).

The data fields requested in the paediatric critical care transport team spreadsheet will include NHS number, hospital number, date of birth, sex, postcode, details of the stabilising hospital (Trust/Health Board and Hospital name), details of transfer arrangements (including the name of the receiving Trust/Health Board), and critical care admission details (where applicable).

Tracking healthcare across multiple organisations

Stabilisation care and admission to critical care may take place in different Trusts/Health Boards, therefore patient care will be tracked across multiple organisations to identify this. To enable us to identify whether a patient was transferred, transfer details will be requested in the patient identification spreadsheet, and the stabilisation questionnaire. If a patient is identified as being transferred and is not included on one of the original patient identification spreadsheets returned to NCEPOD, we will contact the local reporter to confirm whether the patient is known to their organisation for that episode of care using the NHS number and date of birth, prior to uploading the relevant questionnaire.

Clinician questionnaires

Two clinician questionnaires will be used to collect clinical data for this study:

- 1) Stabilisation questionnaire
- 2) Critical care questionnaire

Stabilisation questionnaire

The stabilisation questionnaire will be sent to the clinician responsible for the patient at the time of admission. Questionnaires will be sent to the NCEPOD Local Reporter for dissemination via the online questionnaire system. A reminder will be sent at six weeks and ten weeks where the data is outstanding. Up to 8 patients per hospital will be sampled for inclusion in the study.

Critical care questionnaire

Where applicable, the critical care questionnaire will be sent to the clinician responsible for the patient at the time of admission to their definitive critical care destination. This questionnaire will be sent to the NCEPOD Local Reporter for dissemination via the online questionnaire system. A reminder will be sent at six weeks and ten weeks where the data is outstanding.

5. Case note review

Photocopied case note extracts will be requested for each patient included in the study sample, from arrival at hospital to the point of transfer to the definitive critical care destination or discharge (whichever happens soonest).

Notes requested will include:

- 111 Pathway notes (from Adastra or similar) (where available)
- Ambulance patient report form

- Medical and nursing notes from ED clerking/admission to admission to definitive critical care destination/discharge (whichever happens soonest)
- Critical care notes if admitted as a place of holding during stabilisation before transfer to the definitive critical care destination
- NPEWS/PEWS charts
- Transfer arrangement notes
- Imaging reports
- Anaesthetic chart
- Drug charts
- Discharge summary

If the patient had a long hospital admission, the notes will be limited to the 48 hours prior to deterioration.

We are not requesting any critical care notes from the definitive critical care admission.

Upon receipt at NCEPOD the case notes will be redacted if not already done so prior to sending.

Reviewer assessment form

A multidisciplinary group of reviewers (detailed below) will be recruited to assess the case notes and questionnaires and provide their opinion on what went well and what did not go well during the process of care via the reviewer assessment form.

Table 2 summarises the data sources for significant points along the pathway.

Area of enquiry	Method of data collection	Confidentiality
Acute care	Case notes, clinician questionnaire, organisational questionnaire	Identifiable
	Online surveys	Anonymous

Sample Size

Data source	Target number
Organisational questionnaire	~250
Stabilisation questionnaires	Up to a maximum of 8 per hospital
Case note review	Up to a maximum of 8 per hospital
Patient and parent carer surveys (non-identifiable)	50
Clinician online survey (non-identifiable)	300

Analysis and Review of Data

Reviewers

A multidisciplinary group of reviewers will be recruited to assess the case notes and questionnaires and provide their opinion on what went well and what did not go well during the admission. The reviewer group will comprise intensivists (paediatric and adult – tertiary and secondary care), paediatric transport intensivists, emergency medicine clinicians (paediatric and adult), paediatricians, anaesthetists (paediatric and adult), physicians, critical care, emergency department and paediatric ward nurses, paediatric site practitioners, critical care outreach clinicians, and surgeons (paediatric and adult).

An advert will be sent to Local Reporters to disseminate throughout the relevant departments. It will also be placed on the NCEPOD website and social media channels. Successful applicants will be asked to attend a training day where they will each assess the

same two cases to ensure consistent assessment. A number of meeting dates will be arranged, and each reviewer will then be asked to attend a minimum of a further 4 meetings. NCEPOD staff will ensure there is a mix of specialties at each meeting from across the UK. Each meeting will be chaired by an NCEPOD clinical coordinator who will lead discussion around the cases under review. The meetings will either be held in person in the NCEPOD office, or over Microsoft Teams with secure and temporary access to the case notes for review (not downloadable or printable by the case reviewer). Towards the end of the study the reviewers will be invited to attend a meeting where the data will be presented to and discussed with them. The reviewers will also be sent two copies of the draft report for their comment as this is developed.

Confidentiality and data protection

All electronic data are held in password protected files and all paper documents in locked filing cabinets. As soon as possible after receipt of data NCEPOD will encrypt electronic identifiers and anonymise paper documents. Section 251 approval has been obtained to perform this study without the use of patient consent in England and Wales.

Ethical approval will not be required to undertake this study. Duty of candour is covered by the NCEPOD Cause for Concern policy, which ensure that any cases reviewed as less that satisfactory and as a cause for concern are discussed and action taken where required.

Study outputs

On completion of the study a report will be published and widely disseminated to all stakeholders to encourage local quality improvement (QI) (further details available in the communication plan). In addition to the report, supporting tools will be made available including:

- A summary report and summary sheet
- A patient information leaflet
- Infographics
- The recommendation checklist
- An audit tool
- A slide set
- A guide for commissioners
- Quality improvement tools
- Useful links for patients and parent carers

Examples of good practice will be shared, and additional QI tools will be developed where appropriate. Key messages from the report will be shared via social media.

Following publication, the report findings will be shared at national and local conferences, study days and other events; and papers submitted to journal for consideration for publication.

Data sharing

Post publication of the study there is the potential to share anonymised data sets with interested parties working in the same field. This will be undertaken following a strict process and will ensure the data does not become identifiable in their nature due to small numbers.

Definitions

Paediatric critical care

Level 2 PCCU (Paediatric High Dependency Unit (PHDU))

A discrete area where Level 1 and Level 2 paediatric critical care are delivered.

Other than in specialist children's hospitals, Level 2 Units should be able to provide, as a minimum, acute (and chronic) non-invasive ventilation (both CPAP and BiPAP support) and care for children with tracheostomies and children on long-term ventilation but should not be expected to deliver specialist Level 2 interventions such as ICP monitoring or acute renal replacement therapy. Within specialist children's hospitals, Level 2 units may provide some or all of these additional specialist interventions.

Level 3 PCCU (Paediatric Intensive Care Unit (PICU))

A unit delivering Level 2 and Level 3 paediatric critical care (and Level 1 if required)

Paediatric Critical Care Society. 2021. Quality standards for the care of critically ill of injured children. 6th edition.

Adult critical care

Level 2 critical care (High Dependency Unit (HDU))

Patients needing/requiring:

- Increased levels of observations or interventions (beyond level 1) including basic support for two or more organ systems and those 'stepping down' from higher levels of care.
- Interventions to prevent further deterioration or rehabilitation needs, beyond that of level 1.
- Two or more basic organ system monitoring and support.
- One organ system monitored and supported at an advanced level (other than advanced respiratory support).
- Long term advanced respiratory support.
- Level 1 care for organ support but who require enhanced nursing for other reasons, in particular maintaining their safety if severely agitated.
- Extended post-operative care, outside that which can be provided in enhanced care units: extended postoperative observation is required either because of the nature of the procedure and/or the patient's condition and co-morbidities.
- Patients with major uncorrected physiological abnormalities, whose care needs cannot be met elsewhere.
- Nursing and therapies input more frequently than available in level 1 areas.

Level 3 critical care (Intensive Care Unit (ICU))

- Patients needing advanced respiratory monitoring and support alone.
- Patients requiring monitoring and support for two or more organ systems at an advanced level.
- Patients with chronic impairment of one or more organ systems sufficient to restrict daily activities (co-morbidity) and who require support for an acute reversible failure of another organ system.
- Patients who experience delirium and agitation in addition to requiring level 2 care.
- Complex patients requiring support for multiple organ failures, this may not necessarily include advanced respiratory support.

Intensive Care Society. 2021. Levels of Adult Critical Care Second Edition. Consensus statement.

Timescale

Tilliescale	0	Z	D	Ja	F	3	≥	3	Ju	Ju	Þ	S	0	Z	D	Ja	Ţ	3	≥	3	J	Ju	Þ	S	0	Z	D
	Oct 24	Nov 24	Dec 24	Jan 25	Feb 25	Mar 25	Apr 25	May 25	June 25	July 25	Aug 25	Sept 25	Oct 25	Nov 25	Dec 25	Jan 26	Feb 26	Mar 26	Apr 26	May 26	June 26	July 26	Aug 26	Sept 26	Oct 26	Nov 26	ec 26
	4	14	4	5	5	25	5	25	25	ίň	ίĞ	25	5	.5	5	6	6	26	6	26	26	6	.6	26	6	16	6
Form the Study Advisory Group (SAG)																											
First SAG meeting																											
Draft the protocol																											
Draft the questionnaires																											
Test the data collection method																											
Second SAG meeting																											
Finalise the protocol																											
Finalise the questionnaires																											
Submit final protocol CAG approval																											
Advertise the study																											
Advertise for reviewers																											
Start data collection																											
Reviewer meetings																											
Data analysis																											
Presentation to SAG and Reviewers																											
Presentation to Steering Group																											
Write the report																											
Report production 1st review																											
Report production 2nd review																											
Report production 3rd review																											
Submit report to HQIP																											
Publish the report																											

References

- 1. Dawes J et al. 2014. Stabilisation and Transport of the Critically III Child. *Journal of the Intensive Care Society;* 15(1); 34-42.

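### The case note limit for long admissions, as worded, stops at deterioration and so leaves out the stabilisation that the case reviewers are to assess

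*Protocol*

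**What the plan says.** Under Methods of data collection, 5. Case note review, the general rule asks for extracts "from arrival at hospital to the point of transfer to the definitive critical care destination or discharge (whichever happens soonest". The list of documents that follows repeats this end point for the medical and nursing notes. It also names transfer arrangement notes, the anaesthetic chart and "Critical care notes if admitted as a place of holding during stabilisation before transfer to the definitive critical care destination".

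After the list comes the rule for long stays: "If the patient had a long hospital admission, the notes will be limited to the 48 hours prior to deterioration". The next sentence is a separate exclusion: "We are not requesting any critical care notes from the definitive critical care admission".

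Under Objectives, Clinical issues, the subjects to be explored include "The stabilisation process (including communication, staff involved in the stabilisation process, equipment available", together with intravenous access, respiratory support, decision-making and transfer. The sources given there are: "Data collected from the clinical questionnaire, the reviewer assessment form and clinician survey". Under Reviewer assessment form, a multidisciplinary group works from the case notes and questionnaires and gives its opinion on "what went well and what did not go well during the process of care".

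**The concern.** The long-stay sentence gives one window, and that window lies wholly before deterioration. The study is about what happens once a child has deteriorated. A limit placed there removes the wrong end of the record: it keeps up to two days of earlier ward care and drops the resuscitation, escalation and transfer.

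At stake is the peer review of children who deteriorate late in a long stay. They are in scope, because the inclusion criteria allow the admission to predate the sampling period. If their extracts stop at deterioration, opinions on their stabilisation cannot rest on the notes. If some sites follow the words and others the likely intent, the completeness of the notes will also vary between hospitals for reasons unrelated to care.

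**Working it through.** No sample size, power or error rate is involved, and the protocol has no figure of its own to reproduce. The check sets the statements side by side on one time scale, with deterioration at 0 h.

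1. **Order of events.** The background section lists the organisational failings in sequence: "delays in recognising deterioration, initiating timely interventions, and arranging appropriate transfers". Intervention and transfer follow recognition of deterioration, so stabilisation begins at or after 0 h.

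2. **The windows.**

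| Rule (Case note review) | Start | End |
|---|---|---|
| General | Arrival | Transfer to definitive critical care, or discharge if sooner |
| Long admission, as worded | −48 h | 0 h |
| Long admission, probable intent | −48 h | As in the general rule |

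3. **Overlap with the period under review.** The window from −48 h to 0 h and a stabilisation that starts at 0 h or later share 0 hours. Reading deterioration as a drawn-out episode does not change this, because the time before an episode still ends where the episode starts.

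4. **Consistency with the notes list.** For a ward patient who deteriorates, the holding critical care notes, transfer arrangement notes and any anaesthetic chart from the stabilisation would ordinarily be written after 0 h. The list requests them and the limit shuts them out. Both cannot be followed.

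5. **What remains for these patients.** The case reviewers also see the questionnaires. The stabilisation questionnaire goes to the clinician responsible at the time of admission who, after a long stay, may not be the one who stabilised the child. The critical care questionnaire goes to the receiving clinician, and only where applicable. The clinician survey is anonymous and not linked to other data. So some information on the period survives, but none of it is case note evidence.

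6. **Reach.** The Sample Size table gives about 250 organisational questionnaires and at most 8 case reviews per hospital. If the first figure is taken as the number of hospitals, the ceiling for all case reviews is 250 × 8 = 2,000. The affected patients are some part of whatever total is reached. The protocol gives nothing from which to estimate that part.

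**The case against.** The best defence is that the sentence should be read in its place. It closes a section that has already fixed the end of the extract, and it does not say that this end point is replaced. The condition, a long admission, points to trimming a long lead-in. The list asks for records made during stabilisation and transfer. The separate exclusion of notes from the definitive critical care admission would be redundant for these patients if the extract had already stopped at deterioration. The protocol also promises a test of its methods and tools before the full study, which might expose extracts with no stabilisation record, and the request actually sent to Local Reporters is not among the documents.

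Most of this stands as evidence of intent, and I accept that the intent was probably a 48-hour look-back with the end point unchanged. It does not cure the wording. The sentence says the notes are limited to a stated interval and gives no later end point, and no other part of the protocol supplies one for long stays. Someone assembling extracts could follow it in good faith and leave out the key pages. A method test may catch this, but the protocol does not say that it will look for it.

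The defence is fully right about some stronger conclusions that a reader might draw:

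- **That reviewers would have no evidence on stabilisation.** The documents do not support this, because the questionnaires are part of what they assess.
- **That the reviewer form is the study's main measure.** The protocol lists it alongside the clinical questionnaire and the clinician survey, without ranking them.
- **That a comparison of ward with emergency department stabilisation would be biased.** The protocol plans no such comparison.

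**Conclusion.** The point holds as a fault of wording with a real consequence. As written, the long-admission rule excludes notes of the stabilisation, escalation and transfer that the case reviewers are to judge, and it conflicts with the end point and the notes list in the same section. This is more than a missing detail: it is a stated instruction that yields the wrong extract when followed literally.

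Its size is an unknown number of long-stay patients, for whom reviewers would be left with questionnaires alone for the period that matters. A reader might infer several hundred lost reviews, for example 200 to 500 by applying 10% to 25% to the ceiling of 2,000. The documents do not support that. The share is a guess, the ceiling assumes that every hospital supplies its maximum of 8, and the result requires every site to take the literal reading.

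The conclusion rests on two assumptions: that deterioration means the point at which the child came to need stabilisation, and that at least some sites will act on the words rather than the probable intent.

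**What to change.** State both ends of the window in the long-admission sentence. For long admissions, notes should be requested from 48 hours before deterioration up to the end point already set for all other patients, namely transfer to the definitive critical care destination or discharge, whichever comes first. No new end point or length-of-stay threshold is needed to remove the conflict.

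Use the same wording in the case note request to Local Reporters. If requests have already gone out under the present wording, send a short clarification and ask again for any long-stay extract that stops at deterioration.

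The cost is one sentence in the protocol, the same sentence in the request, and a few extra copied pages for each long-stay patient. The saving in pages that the 48-hour limit was presumably meant to give is kept, because the long lead-in is still cut.
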